### 9.2.2 Drug Screen Results

All laboratory data will be listed including urine drug screen and virology results at screening. Such laboratory parameters include HBsAG, HBcAG, HCV Ab, amphetamines, barbiturates, cocaine, metabolites, opiates, benzodiazepines and cannabinoids.

#### 9.2.3 Pregnancies

A listing of subject pregnancies confirmed by serum pregnancy test will be provided.

### 9.2.4 Nuclear Mitotic Apparatus Protein 22 (NMP22) Testing Results

NMP22 testing results will be summarized for each treatment group, at every assessed time point, as well as presented in a by-subject listing.

### 9.3 Vital Signs and Physical Exams

### 9.3.1 Vital Signs

The vital sign summary and analysis will be based on the recordings of the variables pulse, temperature and respiration rate. Each vital sign parameter at every assessed time point will be summarized using descriptive statistics and presented graphically. Change from baseline will also be summarized, and all vital sign data will be listed.

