9.6 Analysis of Safety

Safety data includes adverse events (AEs), physical exam results, vital signs, ECG results, and clinical lab results including serum chemistry, hematology, and urinalysis. Observed data will be described as counts and percentages for discrete variables and estimation of means, standard deviations, medians, inter-quartile range, minimum and maximum for continuous metrics. All patients will be included in the safety analysis. All safety data will be presented in by-subject listings and included in the clinical trial report.

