9.6.3 Clinical and Laboratory Events and Analyses

Clinical and laboratory metrics are measured at baseline and weeks 2, 6, 12 and 24 during the study. During the treatment extension they are measured every 12 weeks up to a total of 96 weeks. These variables include vital signs (blood pressure, respiration, and temperature), Clinical laboratory (see section 6.7 for a complete list) and ECGs.

Laboratory data will be summarized using Low-Normal-High shift tables. ECG results will be summarized as changes from baseline in intervals. Abnormalities as well as changes from previous assessment will be listed.

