### 4.2 Full Analysis Set

The full analysis set (FAS) will include all subjects in the safety analysis set who have a baseline and at least one post-baseline HbA1c measurement. The full analysis set will be used in efficacy analysis detailed in Section 7. All analyses of the full analysis set will be based on randomly assigned treatment.

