### See table 14.3-2.4 for layout. Use footnotes below.

Note: Baseline is defined as the last available assessment on or prior to the first dose of study medication. The number of subjects with a value at baseline and at the specified visit is displayed.

Source Data: Listing 16.2-9.3

Programming note: use all available timepoints per data following order such as Baseline, Week 2, 6, 12, 18, 24, 36, 48, 60, 72, 84, 96, 97 and 1 week follow-up.

Protocol: THR-1442-C-418 Page x of y

Table 14.3-3.1 Change from Baseline in Vital Signs (Safety Analysis Set)

See table 14.3-2.1 for layout. Use footnote below.

Note: Baseline is defined as the last available assessment on or prior to the first dose of study medication. Source Data: Listing 16.2-10.1

Programming note: use timepoints of Baseline, Week 2, 6, 12, 18, 24, 36, 48, 60, 72, 84, 96, 97 and 1 week follow-up. Use the following parameters: Pulse, Temprature and Respiration Rate (3 parameters).

Table 14.3-4.1 Change from Baseline in ECG Values (Safety Analysis Set)

See table 14.3-2.1 for layout. Use footnote below.

Note: Baseline is defined as the last available assessment on or prior to the first dose of study medication. Source Data: Listing 16.2-10.2

Programming note: use timepoints of Baseline, Week 24, 60, 96, 97 and 1 week follow-up.

Table 14.3-4.2

Overall ECG Interpretations and Abnormal Findings (Safety Analysis Set)

Visit	EGT0001442	Placebo
Assessment	(N=xxx)	(N=xxx)
Screening		
n	xxx	xxx
Normal	xxx (xx.x%)	xxx (xx.x%)
Abormal	xxx (xx.x%)	xxx (xx.x%)
Clinically Significant	xxx (xx.x%)	xxx (xx.x%)
Not Clinically Significant	xxx (xx.x%)	xxx (xx.x%)
Missing	xxx (xx.x%)	xxx (xx.x%)
Week 0		
n	xxx	xxx
Normal	xxx (xx.x%)	xxx (xx.x%)
Abormal	xxx (xx.x%)	xxx (xx.x%)
Clinically Significant	xxx (xx.x%)	xxx (xx.x%)
Not Clinically Significant	xxx (xx.x%)	xxx (xx.x%)
Missing	xxx (xx.x%)	xxx (xx.x%)

Source Data: Listing 16.2-10.3

Programming note: use all available timepoints per data following order such as Screening, Week 0, 24, 60, 96, 97 and 1 week follow-up.

Table 14.3-4.3
ECG Results by Category and Visit
(Safety Analysis Set)

Parameter Visit		0001442 =xxx)		acebo	
ATRIC	( IN	=xxx)	(IV	(=xxx)	
QT Range (msec)					
Week -5					
n		xxx		xxx	
< 450	xxx	(xx.x%)	xxx	(xx.x%)	
>= 450 - < 480	xxx	(xx.x%)	xxx	(xx.x%)	
>= 480 - < 500	xxx	(xx.x%)	xxx	(xx.x%)	
>= 500	xxx	(xx.x%)	xxx	(xx.x%)	
Week 0					
n		xxx		xxx	
< 450	~~~	(xx.x%)		(xx.x%)	
>= 450 - < 480		(xx.x%)		(xx.x%)	

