## Listing 16.2-7.4 Systolic Blood Pressure (mmHg) (Full Analysis Set)

Subject ID/ Age/ Sex/ Race [1]	Visit	Assessment Date	Study Day	Analysis Visit	Post- rescue?	1 st / 2 nd Measure	Mean of 2 Measures	Baseline [2]	Change from Baseline
XXXXXX/ XX/ X/ X	xxx	xxx	xxx	xxx	No	xxxx	xxx	xxx	xxx

 Sex: F=Female, M=Male; Race: W=White, B=Black, A=Asian, I=American Indian or Alaska Native, H=Native Hawaiian or Other Pacific Islander, O=Other.

 Baseline is defined as the last available assessment on or prior to the first dose of study medication.

Protocol: THR-1442-C-418 Page x of y

Listing 16.2-7.5
Diastolic Blood Pressure (mmHg)
(Full Analysis Set)

See Listing 16.2-7.4 for layout. Use footnotes below.

- [1] Sex: F=Female, M=Male; Race: W=White, B=Black, A=Asian, I=American Indian or Alaska Native, H=Native Hawaiian or Other Pacific Islander, O=Other.
- [2] Baseline is defined as the last available assessment on or prior to the first dose of study medication.

Listing 16.2-8.1 Adverse Events (Safety Analysis Set)

See Listing 14.3-1.1 for layout.

[1] Sex: F=Female, M=Male; Race: W=White, B=Black, A=Asian, I=American Indian or Alaska Native, H=Native Hawaiian or Other Pacific Islander, O=Other.

Protocol: THR-1442-C-418 Page x of y

Listing 16.2-8.2 Hypoglycemic Events Supplemental Information (Safety Analysis Set)

Subject ID/ Age/ Sex/ Race [1]	Preferred Term/ Vertatim Text	Treatment Emergent Flag	Onset Date/ Date of Resolution	ADA Severity	Intervention
XXXXXX/ XX/ X/ X	DROWNING/ ACCIDENTAL DROWNING	Y	2009-07-25/ 2009-07-25	xxxxxxx	xxxxxx

 Sex: F=Female, M=Male; Race: W=White, B=Black, A=Asian, I=American Indian or Alaska Native, H=Native Hawaiian or Other Pacific Islander, O=Other.

Protocol: THR-1442-C-418 Page x of y

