#### See listing 16.2-9.1 for layout. Use the following footnote.

- [1] Sex: F=Female, M=Male; Race: W=White, B=Black, A=Asian, I=American Indian or Alaska Native, H=Native Hawaiian or Other Pacific Islander, O=Other.
- [2] NR for Normal Range flag, CS for Clinical Significance flag. H=Above range, L=Below range. CS=Clinically significant, NCS=Not clinically significant.

Protocol: THR-1442-C-418 Page x of y

Listing 16.2-10.1 Vital Signs (Safety Analysis Set)

Treatment: EGT0001442

Subject ID/ Age/ Sex/ Race [1]	Visit	Assessment Date	Study Day	Analysis Visit	Parameter	Result (Unit)
XXXXXX/ XX/ X/ X	xxx	xxxx	xx	xxx	xx	xx (xx)
AA/ A/ A						

 Sex: F=Female, M=Male; Race: W=White, B=Black, A=Asian, I=American Indian or Alaska Native, H=Native Hawaiian or Other Pacific Islander, O=Other.

Programming note: use the following parameters: Pulse, Temprature and Respiration Rate (3 parameters).

Protocol: THR-1442-C-418 Page x of y

Listing 16.2-10.2 ECG Values (Safety Analysis Set)

See listing 16.2-10.1 for layout. Use the following footnote.

[1] Sex: F=Female, M=Male; Race: W=White, B=Black, A=Asian, I=American Indian or Alaska Native, H=Native Hawaiian or Other Pacific Islander, O=Other.

Protocol: THR-1442-C-418

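### SAP 9.3.1 leaves blood pressure out of the Safety Analysis Set vital-sign outputs, so dosed subjects outside the Full Analysis Set have it neither tabulated nor listed (minor)

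*SAP*

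**What the plan says.** Protocol 6.4 defines vital signs as pulse, systolic and diastolic pressure, respiration rate and temperature. Protocol 9.6.3, within the safety analysis, says: "These variables include vital signs (blood pressure, respiration, and temperature". Protocol 9.6 adds: "All safety data will be presented in by-subject listings and included in the clinical trial report". Protocol 9.5 also lists systolic and diastolic pressure as efficacy data, so the variable has two roles.

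SAP 9.3.1 restricts the safety vital signs to "recordings of the variables pulse, temperature and respiration rate". The shell for Table 14.3-3.1 instructs: "Use the following parameters: Pulse, Temprature and Respiration Rate (3 parameters". The shell for Listing 16.2-10.1 says the same: "use the following parameters: Pulse, Temprature and Respiration Rate (3 parameters". Figure 14.3-3.1 takes its data from Table 14.3-3.1 and inherits the restriction. Yet SAP 9.3.1 ends: "Change from baseline will also be summarized, and all vital sign data will be listed".

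Blood pressure is handled in SAP 7.2.4 as a secondary efficacy endpoint. Its listings carry titles such as "Systolic Blood Pressure (mmHg) (Full Analysis Set". SAP 4.2 defines that set as the safety-set subjects "who have a baseline and at least one post-baseline HbA1c measurement", analysed by randomised treatment. SAP 4.1 defines the Safety Analysis Set as randomised subjects with at least one dose, analysed by treatment received.

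**The concern.** The protocol gives blood pressure a safety role as well as an efficacy role, and the SAP carries forward only the efficacy role. Efficacy outputs use a narrower set of subjects and a different rule for assigning treatment. A dosed subject outside the Full Analysis Set would have pulse, temperature and respiration tabulated and listed, but no blood pressure anywhere in the report.

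This matters somewhat more for blood pressure than for another vital sign. Protocol 1.1.2 reports reductions with this drug in earlier work, and Protocol 9.5.2 makes lowering it a formal hypothesis. What is at stake is completeness of the safety record: individual readings, minimum and maximum values, and by-subject listings. The estimated mean effect is not at stake.

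**Working it through.** No figure in the plan needs reproducing. The check is to find every planned blood-pressure output and note the subjects it covers.

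| Output | Blood pressure? | Analysis set |
|---|---|---|
| SAP 6.2 and Tables 14.1-1.4.x, baseline characteristics | No (Protocol 9.4 includes it) | Safety, Full Analysis and Per Protocol |
| Table 14.3-3.1 and Figure 14.3-3.1, vital signs | No | Safety |
| Listing 16.2-10.1, vital signs | No | Safety |
| Tables 14.2-4.1 to 4.5 and 14.2-5.1 to 5.5 | Yes | Full Analysis Set |
| Tables 14.2-4.6 and 14.2-5.6 | Yes | Per Protocol, a subset of the Full Analysis Set |
| Figures 14.2-4.x and 14.2-5.x | Yes | Full Analysis Set |
| Listings 16.2-7.4 and 16.2-7.5 | Yes | Full Analysis Set |

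**Who is left out.** Every row with blood pressure requires Full Analysis Set membership. The subjects with none shown are therefore the Safety Analysis Set minus the Full Analysis Set: those dosed but without a baseline HbA1c or without any post-baseline HbA1c. Baseline tables do not recover them, because the SAP omits blood pressure there too.

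**How many.** The schedule (SAP Table 1) limits this group:

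- The first post-baseline vital signs and the first post-baseline HbA1c both fall at week 2 (Visit 4).
- HbA1c and vital signs are both taken at Visit 15 and at early termination. The visit one week after the last dose applies to early terminators as well as completers.
- SAP 4.2 does not require the post-baseline HbA1c to be on treatment, so a sample at that visit qualifies.

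An early stopper who attends the termination or follow-up visit, and has a baseline HbA1c, normally enters the Full Analysis Set with blood pressure listed. One who attends nothing after randomisation usually has no later reading to lose, only the baseline one. The readings lost are mainly:

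- readings from subjects whose HbA1c sample is missing or failed;
- unscheduled readings from subjects with no post-baseline HbA1c;
- baseline readings of subjects with no later visit.

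The documents give no rate. Assuming 1% to 5% of dosed subjects fall outside the Full Analysis Set:

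- per arm: 0.01 × 150 = 1.5 to 0.05 × 150 = 7.5, about 2 to 8 subjects;
- overall: 0.01 × 300 = 3 to 0.05 × 300 = 15 subjects.

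These count everyone in the gap. Fewer would have a post-baseline reading.

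**Treatment received.** Under SAP 4.4, a subject on the wrong medication for the whole study is analysed as treated for safety and as randomised for efficacy. Because blood pressure sits only in efficacy outputs, that subject's readings would appear only under the randomised arm. This matters only if such a case occurs.

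**The case against.** **Efficacy placement follows the protocol.** Protocol 9.5 lists blood pressure as efficacy data, and Tables 14.2-4.5 and 14.2-5.5 summarise all observed values, including those after rescue. This stands for Full Analysis Set subjects, whose blood pressure is well described. It does not cover the rest of the Safety Analysis Set.

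**The SAP text already promises full listing.** SAP 9.3.1 says all vital sign data will be listed, and SAP 9 puts safety outputs on the Safety Analysis Set. This stands as evidence of intent, but the shells are narrower and programmers work from the shells. The text and shells need to be reconciled.

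**Protocol versions.** The supplied protocol is the original of 02 February 2011. The SAP of 22 November 2011 refers to Amendment 1 (11 April 2011) and to versions dated 18 August and 12 September 2011. Whether the governing version still names blood pressure in 9.6.3 cannot be checked here. The mismatch within SAP 9.3.1 and its listing shell does not depend on that.

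**A stronger reading is tempting but unsupported.** A reader might infer that subjects who stop early because of low pressure are systematically removed from the safety record. The schedule works against this, since HbA1c is drawn at the same termination visit as vital signs. Adverse events of low pressure would also appear in the Safety Analysis Set tables, including those for discontinuation (Table 14.3-1.7 and Listing 14.3-3.1). No planned table counts low readings, so no such rate would be misreported. Nor does Protocol 6.9.7.2 identify a hypotension risk: its examples are urinary symptoms.

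**Conclusion.** The point holds as a minor inconsistency with a small, real gap. No Safety Analysis Set table, figure or listing carries blood pressure, although the supplied protocol treats it as a safety vital sign and SAP 9.3.1 says all vital sign data will be listed. SAP 10 records no change from the planned analyses.

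The gap is confined to dosed subjects without a baseline or post-baseline HbA1c, plus any subject wrongly treated throughout. The 2 to 8 per arm rests wholly on the assumed 1% to 5% and is an upper count for post-baseline readings. The effect on mean blood pressure should be negligible. The primary analysis and the adverse-event reporting are unaffected.

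**What to change.** Add systolic and diastolic blood pressure to the parameters in SAP 9.3.1, Table 14.3-3.1, Figure 14.3-3.1 and Listing 16.2-10.1, on the Safety Analysis Set by treatment received. Change the shell notes from three parameters to five. The same-day averaging rule in SAP 7.2.4 can be reused. Leave the efficacy tables and Listings 16.2-7.4 and 16.2-7.5 as they are.

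The existing table layout gives n, mean, SD, median, minimum and maximum, so the addition restores extreme values and individual readings for every dosed subject with data. The cost is two more parameters in one table, one figure and one listing. SAP Table 1 already schedules vital signs at every visit.

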### 9.3.2 Physical Exam

Final – 22November2011 CONFIDENTIAL Page 28 of 30

The number and percentage of subjects with normal or abnormal findings in each assessment time point will be reported for each treatment groups and body systems. All physical exam data will be listed.

#### **9.4 ECGs**

Each ECG parameter at each assessed time point will be summarized by treatment group using descriptive statistics and presented graphically. Change from baseline will also be summarized. A summary of the number and percentage of subjects on overall ECG interpretation and abnormal findings will be displayed by treatment group.

Additionally, a summary of the number and percent of subjects who experience QT  $\geq$ 450 msec, QT  $\geq$ 480 msec, QT  $\geq$ 500 msec, QTcB  $\geq$ 450 msec, QTcB  $\geq$ 480 msec, QTcB  $\geq$ 500 msec, QTcF  $\geq$ 480 msec, QTcF  $\geq$ 500 msec will be provided,

All ECG data will be listed.

## 10 Changes in the Conduct of the Study or Planned Analyses

Not applicable.

Final – 22November2011 CONFIDENTIAL Page 29 of 30

# Table 14.1-1.1.1 Subject Disposition for Run-in Failures (All Enrolled Subjects)

	Total (N=xxx)
All Enrolled Subjects	xxx
All Randomized Subjects	xxx (xx.x%)
Discontinued Prior to Randomization (Run-in Failures)	xxx (xx.x%)
Reasons Discontinued Prior to Randomization	xxx (xx.x%)
Withdrew Consent	xxx (xx.x%)
Failed Inclusion/Exclusion Criteria	xxx (xx.x%)
Other	xxx (xx.x%)
XXXXXXXXXXXXXXXX	xxx (xx.x%)

Note: Percentages are calculated using the number of subjects enrolled as the denominator.

Source Data: Listing 16.2-2.1

Table 14.1-1.1.2

Subject Disposition for Randomized Subjects

(All Randomized Subjects)

	EGT0001442	Placebo	Total
	(N=xxx)	(N=xxx)	(N=xxx)
Safety Analysis Set	xxx (xx.x%)	xxx (xx.x%)	xxx (xx.x%)
Full Analysis Set	xxx (xx.x%)	xxx (xx.x%)	xxx (xx.x%)
Per Protocol Analysis Set	xxx (xx.x%)	xxx (xx.x%)	xxx (xx.x%)
Completed Active Treatment through Week 24	xxx (xx.x%)	xxx (xx.x%)	xxx (xx.x%)
Discontuned Study before Week 24	xxx (xx.x%)	xxx (xx.x%)	xxx (xx.x%)
Reason for Discontinuing Study before Week 24			
Clinically Significant Change in a Laboratory	xxx (xx.x%)	xxx (xx.x%)	xxx (xx.x%)
Investigator Terminates the Study	xxx (xx.x%)	xxx (xx.x%)	xxx (xx.x%)
Patient Request to be Discontinued from the Study	xxx (xx.x%)	xxx (xx.x%)	xxx (xx.x%)
Protocol Violation	xxx (xx.x%)	xxx (xx.x%)	xxx (xx.x%)
Serious or Intolerable Adverse Event	xxx (xx.x%)	xxx (xx.x%)	xxx (xx.x%)
Sponsor Termiantes the Study	xxx (xx.x%)	xxx (xx.x%)	xxx (xx.x%)
Other	xxx (xx.x%)	xxx (xx.x%)	xxx (xx.x%)
XXXXXXXXXXXXXXXX	xxx (xx.x%)	xxx (xx.x%)	xxx (xx.x%)
XXXXXXXXXXXXXXXX	xxx (xx.x%)	xxx (xx.x%)	xxx (xx.x%)

Note: Percentages are calculated using the number of subjects randomized as the denominator.

Source Data: Listing 16.2-1.1

Table 14.1-1.1.2

Subject Disposition for Randomized Subjects

(All Randomized Subjects)

	EGT0001442 (N=xxx)	Placebo (N=xxx)	Total (N=xxx)
Completed Study	xxx (xx.x%)	xxx (xx.x%)	xxx (xx.x%)
Discontinued Study Early	xxx (xx.x%)	xxx (xx.x%)	xxx (xx.x%)
Reason for Discontinuing Study Early			
Clinically Significant Change in a Laboratory	xxx (xx.x%)	xxx (xx.x%)	xxx (xx.x%)
Investigator Terminates the Study	xxx (xx.x%)	xxx (xx.x%)	xxx (xx.x%)
Patient Request to be Discontinued from the Study	xxx (xx.x%)	xxx (xx.x%)	xxx (xx.x%)
Protocol Violation	xxx (xx.x%)	xxx (xx.x%)	xxx (xx.x%)
Serious or Intolerable Adverse Event	xxx (xx.x%)	xxx (xx.x%)	xxx (xx.x%)
Sponsor Termiantes the Study	xxx (xx.x%)	xxx (xx.x%)	xxx (xx.x%)
Other	xxx (xx.x%)	xxx (xx.x%)	xxx (xx.x%)
XXXXXXXXXXXXXXXX	xxx (xx.x%)	xxx (xx.x%)	xxx (xx.x%)
XXXXXXXXXXXXXXXX	xxx (xx.x%)	xxx (xx.x%)	xxx (xx.x%)

Note: Percentages are calculated using the number of subjects randomized as the denominator.

Source Data: Listing 16.2-1.1

Protocol: THR-1442-C-418 Page x of y

# Table 14.1-1.1.3 Subject Disposition for Randomized Subjects by Country (All Randomized Subjects)

Same layout as Table 14.1-1.1.2. Display 'Country: United States' on the header of the table. Use the following footnote.

Note: Percentages are calculated using the number of subjects randomized as the denominator.

Source Data: Listing 16.2-1.1

Protocol: THR-1442-C-418 Page x of y

Table 14.1-1.2 Subjects Randomized by Country and Study Site (All Randomized Subjects)

Country Site	EGT0001442 (N=xxx)	Placebo (N=xxx)	Total (N=xxx)
XXXXX	xxx (xx.x%)	xxx (xx.x%)	xxx (xx.x%)
XXXXXX	xxx (xx.x%)	xxx (xx.x%)	xxx (xx.x%)
XXXXXX	xxx (xx.x%)	xxx (xx.x%)	xxx (xx.x%)
XXXXX	xxx (xx.x%)	xxx (xx.x%)	xxx (xx.x%)
XXXXXX	xxx (xx.x%)	xxx (xx.x%)	xxx (xx.x%)
XXXXXX	xxx (xx.x%)	xxx (xx.x%)	xxx (xx.x%)
XXXXXX	xxx (xx.x%)	xxx (xx.x%)	xxx (xx.x%)

Source Data: Listing 16.2-1.1

Protocol: THR-1442-C-418 Page x of y

## Table 14.1-1.3 Inclusion/Exclusion Criteria Not Met (All Run-in Failures)

Protocol Version Dated 2011-04-11

IN01:

IN02:

IN03:

···

EX01: EX02:

Protocol Versions Dated 2011-08-18, and 2011-09-12

IN01:

Note: All inclusion and exclusion criteria codes and full text are listed on page 1 of this summary.

Source Data: Listing 16.2-2.1

Protocol: THR-1442-C-418 Page x of y

## Table 14.1-1.3 Inclusion/Exclusion Criteria Not Met (All Run-in Failures)

	Total (N=xxx)
Subjects with Any Inclusion or Exclusion Criterion Deviations	xxx (xx.x%)
Protocol Version Dated 2011-04-11 IN01	xxx (xx.x%)
IN10	xxx (xx.x%)
EX01	xxx (xx.x%)
EX16	xxx (xx.x%)
Protocol Versions Dated 2011-08-18, and 2011-09-12 IN01	xxx (xx.x%)
IN10	xxx (xx.x%)
EX01	xxx (xx.x%)
EX19	xxx (xx.x%)

Note: All inclusion and exclusion criteria codes and full text are listed on page 1 of this summary. Source Data: Listing 16.2-2.1

Table 14.1-1.4.1
Demographics and Baseline Characteristics
(Safety Analysis Set)

	EGT0001442 (N=xxx)	Placebo (N=xxx)	Total (N=xxx)	p-value [1
Age (years)				0.xxxx
n	xxx	xxx	XXX	
Mean (SD)	xx.x (xx.xx)	xx.x (xx.xx)	xx.x (xx.xx)	
Median	xx.x	xx.x	xx.x	
Min, Max	xx, xx	xx, xx	xx, xx	
Gender				0.xxxx
n	xxx	xxx	xxx	
Female	xxx (xx.x%)	xxx (xx.x%)	xxx (xx.x%)	
Male	xxx (xx.x%)	xxx (xx.x%)	xxx (xx.x%)	
Ethnicity				0.xxxx
n	xxx	xxx	xxx	
Hispanic or Latino	xxx (xx.x%)	xxx (xx.x%)	xxx (xx.x%)	
Not Hispanic or Latino	xxx (xx.x%)	xxx (xx.x%)	xxx (xx.x%)	
Child Bearing Potential				0.xxxx
n	xxx	xxx	xxx	
Yes	xxx (xx.x%)	xxx (xx.x%)	xxx (xx.x%)	
No	xxx (xx.x%)	xxx (xx.x%)	xxx (xx.x%)	

 P-value is for testing the null hypotheses that summary statistics (mean or proportion) are equal among treatment groups. All tests are two-sided. \* indicates statistical significance at 0.05 level. Source Data: Listing 16.2-4.1

Table 14.1-1.4.1
Demographics and Baseline Characteristics
(Safety Analysis Set)

	EGT0001442 (N=xxx)	Placebo (N=xxx)	Total (N=xxx)	p-value [1]
Race				0.xxxx
n	xxx	xxx	xxx	
White or Caucasian	xxx (xx.x%)	xxx (xx.x%)	xxx (xx.x%)	
Black or African American	xxx (xx.x%)	xxx (xx.x%)	xxx (xx.x%)	
American Indian or Alaskan Native	xxx (xx.x%)	xxx (xx.x%)	xxx (xx.x%)	
Asian	xxx (xx.x%)	xxx (xx.x%)	xxx (xx.x%)	
Native Hawaiian or Other Pacific Islander	xxx (xx.x%)	xxx (xx.x%)	xxx (xx.x%)	
Other	xxx (xx.x%)	xxx (xx.x%)	xxx (xx.x%)	
XXXXXX	xxx (xx.x%)	xxx (xx.x%)	xxx (xx.x%)	
XXXXXX	xxx (xx.x%)	xxx (xx.x%)	xxx (xx.x%)	
XXXXXX	xxx (xx.x%)	xxx (xx.x%)	xxx (xx.x%)	
Baseline HbA1c Category				0.xxxx
n	xxx	xxx	xxx	
>=7% to <8.5%	xxx (xx.x%)	xxx (xx.x%)	xxx (xx.x%)	
>=8.5% to <=10%	xxx (xx.x%)	xxx (xx.x%)	xxx (xx.x%)	

 P-value is for testing the null hypotheses that summary statistics (mean or proportion) are equal among treatment groups. All tests are two-sided. \* indicates statistical significance at 0.05 level.

Source Data: Listing 16.2-4.1

Table 14.1-1.4.1

Demographics and Baseline Characteristics
(Safety Analysis Set)

	EGT0001442 (N=xxx)	Placebo (N=xxx)	Total (N=xxx)	p-value [1
Height (cm)				0.xxxx
n	xxx	xxx	xxx	
Mean (SD)	xx.x (xx.xx)	xx.x (xx.xx)	xx.x (xx.xx)	
Median	xx.x	XX.X	xx.x	
Min, Max	xx, xx	XX, XX	xx, xx	
Weight (kg)				0.xxxx
n	xxx	xxx	xxx	
Mean (SD)	xx.x (xx.xx)	xx.x (xx.xx)	xx.x (xx.xx)	
Median	xx.x	xx.x	xx.x	
Min, Max	xx, xx	xx, xx	xx, xx	
Body Mass Index (BMI) (kg/m²)				0.xxxx
n	xxx	xxx	xxx	
Mean (SD)	xx.x (xx.xx)	xx.x (xx.xx)	xx.x (xx.xx)	
Median	xx.x	xx.x	xx.x	
Min, Max	xx, xx	xx, xx	xx, xx	

 P-value is for testing the null hypotheses that summary statistics (mean or proportion) are equal among treatment groups. All tests are two-sided. \* indicates statistical significance at 0.05 level.

Source Data: Listing 16.2-4.1

Protocol: THR-1442-C-418 Page x of y

